Chronic prostatitis/chronic pelvic pain syndrome (CP/CPPS) refers to the presence of bothersome pelvic pain symptoms without an identifiable cause¹. Table 1 illustrates the 4 categories of prostatitis per the National Institutes of Health (NIH) classification of prostatitis syndromes. CP/CPPS affects approximately 10–16% of men worldwide^{1–4}. Men of all ages can be impacted, among whom those aged 36–50 years are the most commonly affected⁵. There is no apparent racial predisposition to this disease.

Common symptoms of CP/CPPS include discomfort in the perineum, suprapubic region, and lower urinary tract symptoms⁶. Patients with CP/CPPS also frequently experience a wide array of sexual dysfunctions, including erectile dysfunction (ED), painful ejaculation and premature ejaculation (PE)^{7–11}, on top of symptoms suggestive of negative cognition or emotional consequences¹². The aforementioned symptoms negatively impact upon the patient's quality of life (QoL) to a similar degree or worse than those of congestive heart failure, Crohn's disease, diabetes mellitus or angina^{13, 14}. Because of its high prevalence and lack of effective therapies, direct and indirect costs associated with CP/CPPS are substantial¹⁵. Approximately 25% of men experience loss of work and approximately 50% have reduced leisure time at some point due to CP/CPPS¹⁶. The direct and indirect cost of care in China approaches 8059 CNY per person in 2009¹⁷, and data indicate that in the USA, the total annual cost for patients with prostatitis was US\$4387 in 2006¹⁵.

Unlike acute/chronic bacterial prostatitis, the cause of CP/CPPS is unknown and no well-conducted epidemiologic studies are available to support any particular risk factors¹⁸. The diagnosis of CP/CPPS is mainly based on symptoms. Treatments for CP/CPPS usually include alpha-blockers, antibiotics, nonsteroidal anti-inflammatory drugs (NSAIDs), and phytotherapy. Alpha-blockers and antibiotics have moderate effects on pain, voiding and QoL¹⁹. Both alpha-blockers and antibiotics are recommended for patients with CP/CPPS for less than 1 year, but only antibiotics are recommended in treatment-naïve patients. NSAIDs and phytotherapy are less commonly used, because of lack of research evidence¹⁹. Although advances have been made in research and developing novel treatment options, definitive treatments for CP/CPPS are still lacking¹⁹. Besides, pharmacological interventions are accompanied with adverse effects such as dizziness, nausea, and postural hypotension, which also reduce patients' compliance to treatments²⁰. Previous studies suggest that acupuncture may be a potential treatment for CP/CPPS^{21–25}. However, owing to small sample sizes and other methodological limitations of clinical trials, the efficacy of acupuncture in CP/CPPS remains inconclusive^{19, 26}. In addition, the durable efficacy of the acupuncture is still unclear.²⁷

NIH consensus classification of prostatitis	Definition
(I) Acute bacterial prostatitis	Acute infection of the prostate
(II) Chronic bacterial prostatitis	Chronic or recurrent infection of the prostate
(III) Chronic prostatitis/chronic pelvic pain syndrome	No demonstrated infection
A. Inflammatory	Leukocytes in expressed prostatic secretions, post prostate massage urine, or semen
B. Noninflammatory	No evidence of inflammation
(IV) Asymptomatic inflammatory prostatitis	No subjective symptoms detected, inflammation shown either by prostate biopsy or the presence of leukocytes in EPS/semen during evaluation for infertility or other disorders

NIH, National Institutes for Health

Table 1. NIH consensus classification and definition of 4 categories of prostatitis¹

3. Study Design and Objective

3.1 Objective

The objective of this multi-center, randomized, sham acupuncture-controlled trial is to assess the effectiveness of acupuncture for relieving symptoms of CP/CPPS.

3.2 Primary Hypothesis

The primary study hypothesis is that acupuncture is more effective than sham acupuncture in relieving symptoms of CP/CPPS after treatment and 24 weeks after the cessation of treatment.

3.3 Study Design and Organizations

This is a multicenter, participants-blinded, parallel-group, randomized controlled study conducted in China.

The participants will be recruited in 10 clinical sites, which are Dongfang Hospital Beijing University of Chinese Medicine; Beijing Fengtai Hospital of Integrated Traditional and Western Medicine; West China Hospital of Sichuan University; The Third Affiliated Hospital of Zhejiang Chinese Medical University; The First Affiliated Hospital of Anhui University of Chinese Medicine; Hengyang Hospital Affiliated to Hunan University of Chinese Medicine; The First Hospital of Hunan University of Chinese Medicine; Guangdong Provincial Hospital of Traditional Chinese Medicine; Yantai Hospital of Traditional Chinese Medicine; and Shaanxi Provincial Hospital of Traditional Chinese Medicine. Guang'anmen Hospital, China Academy of Chinese Medical Sciences will be responsible for study design and organization. A data coordination center will be established at China Academy of Chinese Medical Sciences (CACMS) to monitor data management.

3.4 Study Time Frame

The duration of the study for each participant will be 34 weeks: 2 weeks before randomization as eligibility screening and baseline assessment, 8 weeks of treatment period, and 24 weeks of follow up period after the cessation of treatment (Figure 1. Study Design).

[figure not shown]

Figure 1. Study Design

There will be twelve clinical visits:

Visit 1 will be scheduled during weeks -1 and -2 as eligibility screening and baseline assessment;

Visit 2 will be scheduled for baseline assessment and randomization;

Visits 3-10 (20 sessions of treatments) will be scheduled for the 8-week treatment period;

Visits 11 and 12 will be scheduled at weeks 20 and 32, respectively, during 24-week follow-up period.

3.5 Trial Flow Chart

The trial flow chart is shown in Figure 2.

[figure not shown]

Figure 2. Trial Flow Chart

EPS, expressed prostatic secretion; PSA, prostate-specific antigen; NIH-CPSI, National Institutes of Health Chronic Prostatitis Symptom Index; IPSS, International Prostate Symptom Score; HADS, Hospital Anxiety and Depression Scale; IIEF-5, International Index of Erectile Function 5; EQ-5D-5L, European Quality of Life-5 Dimensions-5 Levels.

4. Study Population

4.1 Diagnosis criteria

The diagnosis of CP/CPPS is made according to the NIH CP/CPPS consensus¹, based on medical history, physical examination and a process of exclusion. Urologists are responsible for diagnosis and the differential diagnosis of CP/CPPS.

Participants should have a medical history of persistent discomfort or pain in the pelvic region for at least 3 months in the previous 6 months and an absence of other lower urinary tract pathologies.

Physical examinations will be performed for each participant to detect abnormalities, which include an abdominal examination, digital rectal examination, external genital examination and perineal examination. Abdominal ultrasound will be conducted to assess the condition of other organ and the volume of post-void residual urine. Prostate ultrasound will be conducted to rule out prostatic hyperplasia.

Urinalysis will be performed to rule out urinary tract infections.

A screening “two-glass test”²⁸ will be performed to collect urine specimens and expressed prostatic secretion (EPS) for analysis and culture to rule out possible infection.

A urinary flow rate will be performed for all patients presenting with CP/CPPS to provide information about the function of the lower urinary tract.

Serum prostate-specific antigen (PSA) testing will be completed to screen for the possibility of prostate cancer.

Cystoscopy will be performed in selected patients (decided by urologists) with hematuria, suspicious cytology, irritative and obstructive voiding symptoms.

4.2 Eligibility criteria

Men will be included in the study if they meet the following criteria:

- (1) History of pain perceived in the prostate region and absence of other lower urinary tract pathology for a minimum of three of the past 6 months. In addition, any associated lower urinary tract symptoms, sexual function, and psychological factors should be addressed. Physical examinations, urinary analyses, and urine cultures will be performed for all subjects;
- (2) Age 18 to 50 years;
- (3) NIH-CPSI total score ≥ 15 .

4.3 Exclusion criteria

Men will be excluded from the study if they meet one of the following criteria:

- (1) Other types of prostatitis, such as acute bacterial prostatitis, chronic bacterial prostatitis, or asymptomatic inflammatory prostatitis;
- (2) Urinary tract infection with a urine culture value $>100,000$ colony forming units (CFU)/mL, clinical evidence of urethritis, including urethral discharge or positive culture, diagnostic of sexually transmitted diseases (including gonorrhoea, chlamydia, mycoplasma or trichomonas, but not including HIV/AIDS), symptoms of acute or chronic epididymitis;
- (3) Prostate, penile, testicular, bladder, or urethral cancer, seizure disorder in any medical history;
- (4) Inflammatory bowel disease, active urethral stricture, bladder outlet obstruction, neurologic disease or disorder affecting the bladder, neurologic impairment or psychiatric disorder preventing understanding of consent and self-report scale;
- (5) Overactive bladder, neurogenic bladder, interstitial cystitis, glandular cystitis;
- (6) Organic disease of the urinary system;
- (7) Severe cardiac, lung, cerebrum, liver or renal system disease, or hematopoietic system disease;

- (8) Residual urine volume ≥ 100 mL;
- (9) $Q_{max} \leq 15$ mL/s;
- (10) During previous 4 weeks prior to study participation, used androgen hormone inhibitors (finasteride), alpha-blockers (terazosin, doxazosin mesylate, tamsulosin hydrochloride), antibiotics (ciprofloxacin hydrochloride), or any other prostatitis-specific medication (including herbal and Chinese medicine).

5. Subject Recruitment, Screening, Enrolment, and Group Assignment

5.1 Recruitment and Informed Consent

From October 2017 to December 2019, men with CP/CPPS will be recruited via newspaper, website and hospital posters in 10 centers over China. Patients who show interest in the study and meet the basic criteria of the study will sign the written informed consent form (see Appendix 1 Patient Inform Consent) before the formal screening process. The informed consent form will be reviewed and approved by institutional review boards at Guang'anmen Hospital, China Academy of Chinese Medical Sciences, and individual clinical site.

5.2 Screening and Baseline Assessment

On patients' official Visit 1 (screening visit) to hospital, they will sign the written informed consent form. Research assistants of each site will record their demographic information, course of disease and previous treatments. Urologists are responsible for the diagnosis and the differential diagnosis of CP/CPPS.

Patients will receive a series of procedures to screen for eligibility, which will take approximately two weeks (weeks -1 to -2). To use the funds rationally and for consideration of the convenience of participants, the procedures will be scheduled step by step (Figure 3. Subject Flow Chart), and the eligibility criteria will be verified timely during the process. Those fails in one step will not receive further screening. During the screening periods, participants will not receive any therapy for CP/CPPS.

The screening procedures include (in sequence):

- (1) The medical history, demographic information and previous treatments;
- (2) Chinese-version National Institutes of Health Chronic Prostatitis Symptom Index (NIH-CPSI)^{29, 30};
- (3) Physical examinations (abdominal examination, digital rectal examination, external genital examination and perineal examination);
- (4) Urinalysis
- (5) Abdominal ultrasound and prostate ultrasound will be performed;
- (6) Urine and EPS culture;
- (7) Serum PAS testing;
- (8) Urinary flow rate;
- (9) Cystoscopy, if needed.

Participants who are still eligible after the examinations will complete the baseline outcome assessment questionnaires at home, which include International Prostate Symptom Score (IPSS)^{31, 32}, the Hospital Anxiety and Depression Scale (HADS)³³, International Index of Erectile Function 5 (IIEF-5)³⁴, European Quality of Life-5 Dimensions-5 Levels (EQ-5D-5L)³⁵, and participants' expectation assessment. The NIH-CPSI will completed again.

To eliminate the possible influence of invasive examinations on baseline assessment as much as possible, participants should complete the baseline questionnaires several days after the examinations, preferably on the last day of the screening period. During participants' Visit 2 to hospital, research assistants will collect the questionnaires and verify the eligibility.

Note: Although the eligibility screening and baseline assessment are interpreted as Visit 1 and Visit 2, participants might need to visit the hospital more than twice during the process. The clinical site can arrange the procedures of examinations in accordance with the rapidity of each examination in their own hospital to save participants' time and visits to hospital.

[figure not shown]

Figure 3. Subject Flow Chart

EPS, expressed prostatic secretion; PSA, prostate-specific antigen; NIH-CPSI, National Institutes of Health Chronic Prostatitis Symptom Index; IPSS, International Prostate Symptom Score; HADS, Hospital Anxiety and Depression Scale; IIEF-5, International Index of Erectile Function 5; EQ-5D-5L, European Quality of Life-5 Dimensions-5 Levels.

5.3 Group Assignment

On patients' Visit 2 to hospital, eligible participants will be randomly assigned either to acupuncture group or sham acupuncture group. The randomization will be completed by Acupuncturists. The details of the central randomization will be described below.

6. Randomization and Blinding

6.1 Randomization

In this study, we will use permuted blocks randomization, stratified according to center. A web-response system of Central Randomization System for Clinical Research (designed by Clinical Evaluation Center, China Academy of Chinese Medical Sciences) will be applied in our trial. The allocation sequence will be generated by Institute of Basic Research in Clinical Medicine, China Academy of Chinese Medical Sciences using statistical analysis software SAS 9.4 with "proc plan" program. After production, the sequence will be signed and sealed by the staff who produce it and kept by other staff who take no part in this trial. It will not be allowed to be checked by anyone except the top system administrator.

Only acupuncturists in each center will have access to random numbers and group allocation prior to treatment through the web. Participants will be randomly assigned to the acupuncture or sham acupuncture group at 1:1 ratio.

6.2 Blinding

Research assistants, statisticians, participants, and outcome assessors will be blind to treatment allocations. Only acupuncturists are aware of the group allocation to administrate treatments.

Participants in the sham acupuncture group will receive minimally invasive, superficial needle insertion of 2-3mm at non-acupoints. Treatment protocol will be similar to that of the acupuncture group, and the acupuncturists will be trained to perform the same needling rituals in both groups.

To test the success of blinding, within 5 minutes after treatment (sessions 19 or 20) at week 8, participants will be told that there are two kinds of acupuncture methods, which are the traditional acupuncture where the insertion is relatively deep, and the minimal acupuncture at non-acupoints where the insertion is relatively shallow; and participants will be randomly assigned to receive traditional acupuncture or minimal acupuncture at non-acupoints at 50% chance respectively. Participants will then be asked to answer the question that "Do you think you have received traditional acupuncture in the past weeks?" The participants will be able to choose one of the following options as the answer: "Yes", "No" or "Unclear".

7. Interventions

The intervention scheme of this trial will be based on consensus meeting with acupuncturists and acupuncture experts from CACMS and result of prior study. Sanyinjiao (SP6), Zhongliao (BL33), Shenshu (BL23), and Huiyang (BL35) were selected for the acupuncture treatment group. Based on the theories of traditional Chinese medicine (TCM) and acupuncture, the spleen meridian (SP), kidney meridian (KI), and liver meridian (LI) intersect at Sanyinjiao (SP6), one of the most frequently used acupoints for urological disorders. The urinary bladder meridian (BL) is commonly used for urologic disorders, including pelvic pain, lower urinary tract symptoms, and sexual disorders in both male and female patients. SP6 locates slightly above the medial malleolus, posterior to the tibia where the tibial nerve innervates anatomical structures. Previous research supports the possible beneficial effects of sacral nerve stimulation and tibial nerve stimulation on the severity and frequency of chronic pelvic pain³⁶.

There will be two full-time acupuncturists per center responsible for administration of acupuncture

and sham acupuncture. In general, acupuncturists will be assigned to the same participants throughout the 8-week treatment schedule, except for vacation conflicts and staff turnover. All acupuncturists will be registered TCM practitioners with a clinical acupuncture experience of ≥ 2 years. Disposable acupuncture needles (sizes 0.30×75 , 0.30×40 mm and 0.30×25 mm, Hwato Brand, Suzhou Medical Appliance Factory, Suzhou, China) will be used in this trial.

Participants in both the acupuncture and the sham acupuncture groups will receive 20 sessions of treatment over an 8-week period after baseline (3 sessions in each of the first 4 weeks [ideally every other day], and 2 sessions in each of the remaining 4 weeks [ideally every two or three days]). Each session will last for 30 minutes.

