7.1 Acupuncture

Acupoints of bilateral Zhongliao (BL33), Huiyang (BL35), Shenshu (BL23), and Sanyinjiao (SP6), which will be located according to the WHO Standardized Acupuncture Points Location³⁷ will be used. Zhongliao (BL33) is located in the sacral region, the third posterior sacral foramen. Huiyang (BL35) is located in the buttock region, 0.5 proportional bone (skeletal) cun (B-cun) lateral to the extremity of the coccyx. Shenshu (BL23) is located in the lumbar region, at the same level as the inferior border of the spinous process of the second lumbar vertebra (L2), 1.5 B-cun lateral to the posterior median line. Sanyinjiao (SP6) is located on the tibial aspect of the leg, posterior to the medial border of the tibia, 3 B-cun superiors to the prominence of the medial malleolus.

With patients in a prone position in relaxation, acupuncturists will use 75% alcohol pads to sterilize the skin around the acupuncture points and then insert Hwato-brand disposable acupuncture needles (sizes 0.30×75 and 0.30×40 mm) into the acupuncture points. For bilateral Zhongliao (BL33), the needle will be inserted approximately 50–60 mm with a 30° – 45° angle in an inferomedial direction. For Huiyang (BL35), the needle will be inserted approximately 50–60 mm in a slightly superolateral direction. For Shenshu (BL23) and Sanyinjiao (SP6), the needles will be inserted vertically with a depth of 25–30 mm. For acupuncture at BL23, BL35 and SP6, needle insertion will be followed by acupuncture manipulation of lifting and thrusting combined with twirling and rotating to reach *deqi*, which is defined as the sensation of aches, soreness, swelling, heaviness or numbness in the needle location region³⁸. Manipulations will be performed once every 10 minutes, 30 seconds each time. Immediately after needle removal, the acupuncturist will gently press the needled skin area with dry sterilized cotton balls to avoid bleeding.

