7.2 Sham Acupuncture

The participants in the sham acupuncture group will receive minimally invasive, superficial needle insertion of 2–3 mm at bilateral sham BL23, BL33, BL35 and SP6 (non-acupuncture points lateral to the corresponding acupoints, 15 mm to BL23, BL33 and BL35; 10 mm to SP6). Treatment protocol will be similar to that of the acupuncture group, but Hwato-brand disposable acupuncture needles (size 0.30×25 mm) will be inserted at sham acupoints with depths of 2–3 mm without manipulation³⁹.

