7.3 Standardization of Treatment

Guang'anmen Hospital will supply single-use, sterile, and disposable acupuncture needles for each participating site.

Two certified acupuncturists will be needed in each site to perform all the treatments, while the 20 sessions of treatment for each participant should be completed by one specific acupuncturist. All acupuncturists in this trial are required to have completed their professional training in acupuncture in universities of Chinese medicine with more than 2 years clinical experience.

To improve the consistency of treatments, acupuncturists at each site will receive trial-specific

(standardized operation procedure) training at the project launching session. The training will include detailed acupuncture points locations and manipulation methods in both the acupuncture and sham acupuncture groups. A video showing detailed information on how to perform the acupuncture and sham acupuncture will also be provided.

To avoid the inadvertent unblinding, acupuncturists will not tell anyone else the treatment allocation. The contacts between acupuncturists and participants should be as short as possible.

The acupuncturists will be instructed to follow standardized operating procedure:

Step 1:

The participant is piloted by research assistant to hospital bed, which was screened-off separately one-by-one. Their companions will be guided to wait outside the clinic, if any. The specific acupuncturist accepts the patient and asks the participant to take a rest. After a short while, acupuncturist instructs the patient to lie prone on the bed, with lumbosacral and lower shin areas exposed, and tell the participant that a 30-minute treatment will be given.

Before the first session of treatment, participants will be told that they may receive either the traditional acupuncture or sham acupuncture group, and they may not have sensation during the 30-minute retention of acupuncture needles out of body adaptation.

Step 2:

After sterilization, the acupuncturist will start to conduct administration according to treatment protocol. The acupuncture group will receive deep insertion of needles at acupuncture points, while the sham acupuncture group will receive superficial insertion of needles at non-acupuncture points.

Step 3:

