After insertion of needles at appropriate areas, acupuncturist will conduct the first needle manipulation in the acupuncture group for 30 seconds, while in the sham acupuncture group, acupuncturists will hold the handles of acupuncture needles gently for 30 seconds without manipulations.

Step 4:

After 10 minutes, acupuncturist will conduct the second needle manipulation in the acupuncture group for 30 seconds, while in the sham acupuncture group, acupuncturists will hold the handles of acupuncture needles gently for 30 seconds without manipulations.

Step 5:

After another 10 minutes, acupuncturist will conduct the third needle manipulation in the acupuncture group for 30 seconds, while in the sham acupuncture group, acupuncturists will hold the handles of acupuncture needles gently for 30 seconds without manipulations.

Step 6:

After another 10 minutes, acupuncturist will remove the needles.

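### The week-8 blinding test tells participants a real difference between the arms before the week-32 co-primary, and possibly before the week-8 one: an avoidable risk to blinding, not shown unblinding

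*Combined protocol and SAP*

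**What the plan says.** Protocol 6.2 places the blinding test at week 8, within 5 minutes after session 19 or 20. Participants hear that there are two methods, "the traditional acupuncture where the insertion is relatively deep, and the minimal acupuncture at non-acupoints where the insertion is relatively shallow", each with an even chance. Then: "Participants will then be asked to answer the question" of whether they believe they had the traditional kind (Yes, No or Unclear). Protocol 8.2.3 has outcome assessors do this at hospital. SAP 6.3.4 analyses the answers with the James and Bang indices.

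The description matches the interventions. Protocol 7.1: "For bilateral Zhongliao (BL33), the needle will be inserted approximately 50–60 mm". The same depth applies to BL35, and 25–30 mm applies to BL23 and SP6. Protocol 7.2: the sham needles "will be inserted at sham acupoints with depths of 2–3 mm without manipulation".

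Before session 1, protocol 7.3 has participants told that "they may receive either the traditional acupuncture or sham acupuncture group, and they may not have sensation during the 30-minute retention". That wording mentions neither depth nor site.

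The co-primary outcomes (protocol 8.1.1) are response at weeks 8 and 32 on the self-reported NIH-CPSI. Protocol 8.2.4 repeats the questionnaires at weeks 20 and 32.

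**The concern.** The script gives each participant a criterion for judging which arm he is in, and the trial then relies on his self-report for a further 24 weeks. A man who concludes that he had the shallow kind may report less improvement. The week-32 co-primary is exposed, and it carries the long-term efficacy that SAP section 2 emphasises. If the week-8 form is completed after the script, that co-primary is exposed too.

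The planned indices use one guess taken straight after the cue. They capture immediate unblinding. They cannot show a view that changes during session 20 (in men tested after session 19) or during follow-up, and no later check is planned.

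**Working it through.** **1. Is the cue a true contrast?** Yes. The acupuncture arm is needled at 25–60 mm, the sham arm at 2–3 mm at non-acupoints. Manipulation and needle size also differ, but the script does not mention them.

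**2. Does the script come before the outcomes?**
- *Weeks 20 and 32:* yes, always.
- *Week 8:* not settled. Sessions: 3 × 4 + 2 × 4 = 20, so sessions 19 and 20 both fall in week 8.
  - Pointing to an earlier form: protocol 10.5(5) has participants bring the notebook to hospital themselves during the treatment period, and only the week-20 notebook may be mailed. A form brought to session 20 precedes a script given after that session.
  - Pointing to a later form: protocol 8.2.3 has the notebook completed at home and brought the following week, and SAP 6.3.3 calls the measure end of treatment. Section 7 schedules "2 sessions in each of the remaining 4 weeks [ideally every two or three days", so a man tested after session 19 still has session 20 to come.
  - Table 2, in the text available, has no row for the blinding test.

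**3. The plan's own figures.** The planning rates are 63.7% and 46.7% (protocol 11.1). The odds ratio is (0.637/0.363)/(0.467/0.533) = 2.00, as stated. The two-proportion formula (two-sided 0.05, 90% power) gives 178 per group, or 190 with continuity correction. Then 190 × 1.15 = 218.5, rounded up to 219 per group or 438 in total, close to the stated 440.

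**4. Illustration of size.** The documents give neither the share of men newly unblinded nor any reporting shift. Assume gap g = share of the sham arm whose belief changes × change in their chance of reporting response. For example, 20% × 10 points = 2 points.

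Further inputs:
- n = 220 per group, all randomised (SAP 6.2).
- All rates multiplied by 1.00 or 0.85, because men who discontinue without a score count as non-responders (SAP 6.3.3) and protocol 11.1 allows 15% for dropout.
- 50% response in both arms where there is no effect (assumed).
- Correlation of 0.3 to 0.7 between the two test statistics (assumed).
- A simple two-proportion test in place of the planned mixed model.

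The probability of significance in favour of acupuncture at one time point is Φ[((pA − pS) − 1.96·SE0)/SE1], where SE0 = √(2p̄(1 − p̄)/n) and SE1 = √((pA(1 − pA) + pS(1 − pS))/n). Joint success is taken from a bivariate normal distribution, because protocol 11.1 requires both time points to be positive.

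- Week 8 at the planning rates: (0.170 − 1.96 × 0.0474)/0.0467 = 1.65, which gives 95.0%. With factor 0.85 it is 86.2%.
- Week 32, 50% v 48%: (0.02 − 0.0934)/0.0477 = −1.54, which gives 6.2%. With factor 0.85, −1.60 gives 5.5%.
- Week 32, 50% v 52%: (−0.02 − 0.0934)/0.0477 = −2.38, which gives 0.9%. With factor 0.85, −2.32 gives 1.0%.

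Probability that the trial is declared successful at both time points:

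| Scenario | No gap | 2 points favouring acupuncture | 2 points the other way |
|---|---|---|---|
| True week-8 effect, none at week 32; week 32 shifted | 2.4–2.5% | 5.3–6.2% | 0.9–1.0% |
| No true effect; only week 32 shifted | 0.2–0.8% | 0.4–1.4% | 0.1–0.5% |
| No true effect; both shifted (every week-8 form after the script, an upper case) | 0.2–0.8% | 0.8–2.6% | below 0.3% |

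In the second row the result cannot exceed 2.5% for any gap, because week 8 must also be significant in favour of acupuncture and that happens 2.5% of the time when there is no effect.

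**The case against.** Four arguments carry weight.

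- *Depth and site may be old news.* The consent pages were not available, and 7.3 shows only what is said before session 1. If consent already described both, most of the added risk goes. This stands as a condition on the point.
- *The sham is well masked.* Treatment is given "With patients in a prone position in relaxation", participants are warned that they may feel nothing, and at the manipulation times in the sham arm "acupuncturists will hold the handles of acupuncture needles gently for 30 seconds without manipulations". A sham participant may well conclude that his needling was deep. This stands: the direction of any bias is open.
- *The notebook may come in first.* Protocol 10.5(5) favours this for week 8. It does not settle the order, because 8.2.3 and the session-19 option remain.
- *A guess needs defined terms.* The script presents both methods as kinds of acupuncture and explains the term used in the question, whereas sham is arguably the more loaded word. This stands in part, but the question itself uses only the word traditional, which participants already know from 7.3.

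A reader might infer that the script unblinds participants, or that it tilts week 32 towards acupuncture. The documents support neither: they do not show that men can judge depth by sensation, or how belief would alter reporting. Larger gaps give more striking figures. Five points gives 13.9–18.1% in the table's first scenario, but that needs, for instance, half the sham arm newly and correctly persuaded, with a 10-point fall in reported response, plus a full week-8 effect and none at week 32.

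**Conclusion.** The point holds as an avoidable risk to blinding, worth a small change to the plan. The script discloses one real contrast before the week-20 outcomes and the week-32 co-primary, and the plan does not ensure that the week-8 co-primary is recorded first.

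The likely effect is small unless many men change their belief. The requirement that both time points be positive limits the harm: bias at week 32 alone cannot make the trial succeed. It matters mainly when a true week-8 effect does not last, because week 32 then decides the result. The illustrative figures rest on assumed gaps and run in both directions. Confidence is medium, chiefly because the consent text cannot be checked.

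It would go too far to say that blinding fails at weeks 20 and 32. What can be said is that it is not re-tested after week 8.

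**What to change.** In protocol 6.2, 8.2.3 and Table 2:

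1. Drop the session-19 option. Give the blinding test only after session 20 and after the week-8 notebook, completed at home as usual, has been handed in. If it has not been handed in, delay the test. Do not have the form filled in at hospital after needling, because baseline and weekly forms are completed at home (5.2, 8.2.3).
2. At week 8, ask the existing Yes/No/Unclear question without the description of depth and site.
3. If the descriptive version is wanted, give it at Visit 12 after the week-32 notebook is handed in, as supplementary information.
4. If the description stays at week 8, keep the order in item 1 and report that blinding was not re-tested after week 8.

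Cost: a revised assessor script, a stated order of procedures and a new row in Table 2. Men who bring the notebook to session 20 need no extra visit, and week 32 is already attended in person for urinary flow (8.2.4).

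Downsides: the 5-minute limit must be relaxed, and a late notebook means a later guess. There will probably be more Unclear answers, which can make blinding look better, and the week-8 guess becomes somewhat harder to interpret. A week-32 guess is coloured by symptom course and misses dropouts.
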